7.1.1.8.2 Concomitant Vaccinations

No other investigational compound or device may be administered at any time during this study without prior approval by the SPONSOR.

¹ Needles provided in Prevnar 13TM blister packages may also be used.

² Per investigator discretion, dose 4 can be administered in the deltoid muscle instead of the anterolateral thigh muscle; if given in the deltoid muscle, the needle length should be 5/8 to 1 inch (a 5/8 inch needle may be used only if the skin is stretched tight, subcutaneous tissue is not bunched, and injection is made at a 90-degree angle).

The study vaccines will be administered at approximately 2, 4, 6, and 12 to 15 months of age. Other pediatric vaccines will be administered concomitantly according to the mandated schedule in the site's country/region. These concomitant non-study vaccinations will be recorded on the appropriate eCRF. Combination MMRV vaccines should not be given in this study; however, MMR and Varicella vaccines are permitted if administered concomitantly in 2 separate limbs.

Concomitant vaccines (oral or injectable) should be administered on the same day as study vaccine. Concomitant oral vaccines may be administered prior to the study vaccine and other injectable concomitant vaccines. Precautions must be taken to prevent choking during the administration of oral vaccines. Concomitant injectable vaccines should be administered after the study vaccine. To avoid any confounding results, non-study injectable vaccines should not be administered in the same limb as study vaccine. Documentation of which limb was used for the administration of study vaccine should be recorded on the appropriate eCRF. As we are requesting the reporting of injection-site adverse experiences from the study vaccine (and not from the concomitant vaccines), this information should also be recorded on the VRC to inform the parent/legal guardian of the appropriate limb to monitor for adverse experiences ONLY related to the study vaccine.

During the influenza season, it is anticipated that trial subjects 6 months of age and older may be given an influenza vaccine. Influenza vaccine should be administered either 14 days prior to or 30 days after the administration of the trial vaccine.

7.1.1.9 Dispense Electronic Vaccination Report Cards

The vaccination report card was developed to be administered electronically via a hand-held device. This item was structured as recommended in the final FDA Patient Reported Outcome (PRO) Guidance. The investigator or delegate will train the subject's parent/legal guardian in the use of the electronic vaccination report card prior to dispensing it at Visit 1. Body temperatures, injection-site AEs, VRC-prompted systemic complaints, other complaints or illnesses, and medications will be recorded on the VRC throughout the study. The investigator or delegate will review the data captured on the VRC with the parent/legal guardian at Visit 2 through Visit 6.

Interruptions from the protocol specified vaccination require consultation between the investigator and the Sponsor and written documentation of the collaborative decision on subject management.

7.1.2 Clinical Procedures/Assessments

7.1.2.1 Physical Examinations

A full physical examination will be performed at Visits 1, 2, 3, and 5.. Any clinically significant abnormality will be recorded on the appropriate eCRF.

The full physical examination procedures include obtaining vital signs (heart rate, respiratory rate, and body temperature), auscultation of the heart and lung, and examination of the abdomen, an assessment of the head, eyes, ears, nose and throat (HEENT), skin, lymph nodes, neurological system, and musculoskeletal system.

Findings related to the physical examinations should be documented in the subject chart/source documentation.

7.1.2.2 Temperature

Pre-vaccination rectal temperatures will be taken by trial staff at Visits 1, 2, 3, and 5. Subjects who have febrile illness (rectal temperature $\geq 38.1^{\circ}\text{C}$ [$\geq 100.5^{\circ}\text{F}$] or axillary temperature $\geq 37.8^{\circ}\text{C}$ [$\geq 100.0^{\circ}\text{F}$]) occurring at or within 72 hours of Visits 1, 2, 3 and 5 must be rescheduled. Rectal is the preferred method of obtaining subject's temperature. Axillary (underarm) is an acceptable method but temperature needs to be confirmed by rectal measurement. If an axillary temperature is performed and is reported to be $\geq 37.8^{\circ}\text{C}$ ($\geq 100.0^{\circ}\text{F}$), it must be confirmed with a rectal temperature. In this case, both axillary and rectal temperatures must be recorded on the VRC. Temperature readings should be taken at approximately the same time each day. Use of temporal or tympanic thermometers to collect temperature for this study is prohibited.

The subject's parent/legal guardian will be asked to record a rectal temperature reading on the VRC from Day 1 through Day 7 following each vaccination. Temperature measurement must be recorded in the VRC if fever is suspected during Day 8 through Day 14.

7.1.2.3 Assess Adverse Experiences

Study subjects will be observed for 30 minutes postvaccination for any immediate AEs. The time at which the event occurred within the 30 minute timeframe, as well as the event itself and resolution of the event must be recorded on the appropriate eCRF. Instructions on completing the VRC will be reviewed with each study subject's parent/legal guardian. Injection-site and systemic AEs occurring Day 1 through Day 14 following each vaccination will be recorded by the subject's parent/legal guardian on the electronic VRC; this includes VRC-prompted injection-site AEs (redness, swelling, hard lump, and pain/tenderness) and VRC-prompted systemic AEs (irritability, drowsiness, appetite lost, hives or welts). See Section 7.2 for detailed information concerning the assessment and recording of AEs.

7.1.3 Laboratory Procedures/Assessments

Details regarding specific laboratory procedures/assessments to be performed in this trial are provided below. The total amount of blood/tissue to be drawn/collected over the course of the trial (from pre-trial to post-trial visits), including approximate blood/tissue volumes drawn/collected by visit and by sample type per subject can be found in Section 12.4.

7.1.3.1 Laboratory Safety Evaluations (Hematology, Chemistry and Urinalysis)

There are no laboratory safety evaluations required by the protocol.

7.1.3.2 Blood Collection for Immunogenicity Assays

Subjects will have blood drawn (approximately 4-5 mL) at 3 time points: (1) approximately 1 month following the third study vaccination (PD3), (2) immediately prior to administration of the fourth study vaccination, and (3) approximately 1 month following the fourth study vaccination (PD4). Sera will be used to measure vaccine-induced pneumococcal-specific immune responses (IgG and opsonophagocytic killing activity [OPA]). These serum samples will be assayed using the Meso-Scale Discovery MSD Pn ECL assay, which was developed by Merck & Co., Inc. for the measurement of pneumococcal capsular polysaccharide IgG antibodies. Serum samples will also be assayed using a 4-Fold Multiplex Opsonophagocytic Assay which Merck has developed and implemented in collaboration with [REDACTED]

[REDACTED]^{PPD}. If a serum sample does not have enough volume for both the IgG and OPA testing, the IgG testing will take priority. OPA will be evaluated in approximately 50% of subjects enrolled at US investigator sites with sufficient PD3 sera available to perform both the PnECL and the OPA testing on all 15 serotypes in V114. OPAs will be conducted at pre-dose 4 and at PD4 for all of the subjects who had PD3 OPAs performed and for which there is sufficient serum. Any remaining sera will be retained for future biomedical research (e.g., pneumococcal assay development) providing the future biomedical research (FBR) consent has been signed.

Pneumococcal Electrochemiluminescence (Pn ECL) Assay

The purpose of the Pn ECL assay is to detect serum IgG antibody to the pneumococcal polysaccharides (PnPs) serotypes 1, 3, 4, 5, 6A, 6B, 7F, 9V, 14, 18C, 19F, 19A, 22F, 23F, and 33F before and after vaccination with PnPs containing vaccine(s). The serotypes are assayed in a group of 7 (types 1, 5, 6A, 7F, 19A, 22F, 33F) and a group of 8 (types 3, 4, 6B, 9V, 14, 18C, 19F, 23F). Antibodies to these serotypes are measured in mass units (μ g/mL) read from a standard curve prepared from a pool of adult serum, collected postvaccination with a PPV23 and referred to as 007sp.

The assay is based on the MSD™ technology which employs multi-spot microtiter plates fitted with a series of electrodes associated with the bottom of the well. Serotype-specific PnPs are spotted to the MSD™ plates and used as the solid phase antigen. Experimental, control, and standard curve sera are pre-adsorbed with pneumococcal cell wall polysaccharide (CPs) and non-vaccine heterologous serotype PnPs (types 25 and 72) to reduce the nonspecific antibody response in the assay, and subsequently incubated in the PnPs antigen-coated wells. Anti-PnPs, which bind to the solid phase PnPs, are subsequently detected with a ruthenium-labeled anti-human IgG conjugate. Plates are read by measure of the chemiluminescent signal emitted from the ruthenium tag upon electrochemical stimulation initiated at the electrode surfaces of the microplates. The intensity of the luminescence is directly proportional to the amount of anti-PnPs in the sample.

Standard curves are prepared from the human Pneumococcal Standard Reference Serum, 007sp (Center for Biologics Evaluation and Research, U.S. FDA). The following standard and controls are run in each assay: (a) a 12-point standard curve which includes a serum diluent blank and an 11-point, 2.5-fold dilution series of 007sp that begins with an initial dilution of 1:400; (b) two different dilutions (1:1000 and 1:10,000) of Giebink serum 16 (G16) and one dilution (1:1000) of Giebink serum 5 (G5), both individual human immune sera obtained after vaccination with PPV23 by [REDACTED]; (c) a serum sample from a previous Merck clinical trial tested at 1:10,000 dilution.

Clinical testing on the Pn ECL assay will be performed at Merck Research Laboratories (MRL) or its designated partners that are qualified to perform the assay.

Multiplex Opsonophagocytic Assay (MOPA-4)

The 4-Fold Multiplexed Opsonophagocytic Killing Assay for antibodies against *Streptococcus pneumoniae* (MOPA-4) is used to measure sera of patients vaccinated with multivalent pneumococcal vaccines for antibody titers (opsonic activity/killing) against the capsular polysaccharides for specific *S. pneumoniae* serotypes. The method is multiplexed permitting testing of 4 serotypes per run, eliminating excessive use of infant sera. The assay utilizes complement (baby rabbit source), a critical component, which requires qualification prior to use in the MOPA-4. The opsonophagocytic killing assay (OPA) also utilizes HL-60 human Promyelocytic Leukemia cells which are transformed into phagocytes for this assay. Complement is added in addition to bacterial strains (pneumococcal serotypes 1, 3, 4, 5, 6A, 6B, 7F, 9V, 14, 19A, 18C, 19F, 22F, 23F, and 33F; strains tested in groups of 4) and patient sera. The ability of antibodies in patient sera, at a series of dilutions, to initiate the killing of the pneumococcal bacteria is the basis for assignment of antibody titer of the sample. The opsonization titers (OT) are defined as the serum dilution that kills 50% of bacteria and are determined using a linear interpolation algorithm. The results are reported as the reciprocal of the dilution. The MOPA-4 was developed and published by [REDACTED]

Merck has been involved in the development and implementation of the MOPA-4 in collaboration with [REDACTED] and with [REDACTED] Both labs are qualified to generate clinical results and one of them will support MOPA-4 testing for this study.

Clinical testing on the MOPA assay will be performed at Merck Research Laboratories (MRL) or its designated partners that are qualified to perform the assay.

7.1.3.3 Future Biomedical Research Samples

The following specimens are to be obtained as part of Future Biomedical Research:

- DNA for future research
- Leftover serum samples collected in the main study.

7.1.4 Other Procedures

7.1.4.1 Withdrawal/Discontinuation

Subjects who discontinue/withdraw from vaccination prior to completion of the vaccination regimen should be encouraged to continue to be followed for all remaining study visits.

When a subject discontinues/withdraws from participation in the trial, all applicable activities scheduled for the final trial visit should be performed at the time of discontinuation. Any adverse events which are present at the time of discontinuation/withdrawal should be followed in accordance with the safety requirements outlined in Section 7.2 - Assessing and Recording Adverse Events. Any infant subject fails to achieve adequate serologic responses, as described in Rescue Medications & Supportive Care Section 5.6, will be discontinued from the trial prior to administering the additional dose of licensed pneumococcal conjugate vaccine.

7.1.4.1.1 Withdrawal From Future Biomedical Research

A subject's consent for Future Biomedical Research may be withdrawn by the subject's legally acceptable representative. A subject's consent may be withdrawn at any time by contacting the principal investigator for the main trial. If medical records for the main trial are still available, the investigator will contact the Sponsor using the designated mailbox ([contact]). Subsequently, the subject's consent for Future Biomedical Research will be withdrawn. A letter will be sent from the Sponsor to the investigator confirming the withdrawal. It is the responsibility of the investigator to inform the subject of completion of withdrawal. Any analyses in progress at the time of request for withdrawal or already performed prior to the request being received by the Sponsor will continue to be used as part of the overall research trial data and results. No new analyses would be generated after the request is received.

In the event that the medical records for the main trial are no longer available (e.g., if the investigator is no longer required by regulatory authorities to retain the main trial records) or the specimens have been completely anonymized, there will no longer be a link between the subject's personal information and their specimens. In this situation, the request for specimen withdrawal cannot be processed.

7.1.4.1.2 Failure To Return For Scheduled Visits and/or Unable to Contact The Subject

If a subject fails to return to the clinic for a required study visit and/or if the site is unable to contact the subject, the following procedures are to be performed:

- The site must attempt to contact the subject and reschedule the missed visit. If the subject is contacted, the subject should be counseled on the importance of maintaining the protocol-specified visit schedule.

- The investigator or designee must make every effort to regain contact with the subject at each missed visit (e.g. phone calls and/or a certified letter to the subject's last known mailing address or locally equivalent methods). These contact attempts should be documented in the subject's medical record.
- Note: A subject is not considered lost to follow up until the last scheduled visit for the individual subject. The amount of missing data for the subject will be managed via the pre-specified data handling and analysis guidelines.

7.1.4.2 Subject Blinding/Unblinding

When the investigator or delegate needs to identify the vaccine used by a subject and the dosage administered in case of emergency e.g., the occurrence of serious adverse experiences, he/she will contact the emergency unblinding call center by telephone and make a request for emergency unblinding. As requested by the investigator or delegate the emergency unblinding call center will provide the information to him/her promptly and report unblinding to the sponsor. Prior to contacting the emergency unblinding call center to request unblinding of a subject's treatment assignment, the investigator or delegate must enter the intensity of the adverse experiences observed, the relation to study vaccine, the reason thereof, etc., in the medical chart etc. Subjects whose treatment assignment has been unblinded by the investigator/delegate and/or non-study treating physician must be discontinued from study vaccine, but should continue to be monitored in the trial.

Additionally, the investigator must go into the IVRS system and perform the unblind in the IVRS system to update vaccine disposition. In the event that the emergency unblinding call center is not available for a given site in this trial, IVRS/IWRS should be used for emergency unblinding in the event that this is required for subject safety.

In the event that unblinding has occurred, the circumstances around the unblinding (e.g., date, reason and person performing the unblinding) must be documented promptly, and the Sponsor Clinical Director notified as soon as possible. Only the principal investigator or delegate and the respective subject's code should be unblinded. Other trial site personnel and Sponsor personnel directly associated with the conduct of the trial should not be unblinded. Subjects whose treatment assignment has been unblinded by the investigator/delegate and/or non-study treating physician must be discontinued from study vaccine, but should continue to be monitored in the trial.

7.1.4.3 Domiciling

Infant subjects will report to the Clinical Research Unit (CRU) on the day of the administration of study vaccine (Visit 1, 2, 3, and 5) and remain in the unit for 30 minutes postvaccination. At the discretion of the investigator, subjects may be requested to remain in the CRU longer. Infants will return to the CRU at Visits 4 and 6 for blood draws.

7.1.4.4 Calibration of Critical Equipment

The investigator or qualified designee has the responsibility to ensure that any critical device or instrument used for a clinical evaluation/test during a clinical trial that provides important information about inclusion/exclusion criteria and/or safety or efficacy parameters shall be suitably calibrated and maintained to ensure that the data obtained is reliable and/or reproducible. Documentation of equipment calibration must be retained as source documentation at the trial site.

Critical Equipment for this trial includes:

- Refrigerators
- -20° freezers
- Centrifuges

7.1.5 Visit Requirements

Visit requirements are outlined in Section 6.0 - Trial Flow Chart. Specific procedure-related details are provided above in Section 7.1 - Trial Procedures.

7.1.5.1 Screening

Screening procedures will be performed at Visit 1. A separate screening visit is not required.

7.1.5.2 Vaccination Visits

Subjects will be required to come to the clinic for 6 visits. See Section 6.0 for details.

7.1.5.3 Discontinued Subjects Continuing to be Monitored in the Trial

Subjects who discontinue from the trial after visits 1, 2, 3 or 5 (vaccination visits) but agree to continue to be monitored in the trial will be requested to return for a final monitoring visit. Subjects who discontinue after Visit 4 (due to lack of efficacy or other reasons) are not required to continue to be monitored and will not be requested to return for a final monitoring visit.

Subjects returning for a final monitoring visit will be required to return to clinic approximately 14 days after the last vaccination for the post-trial visit. The following will be completed at this visit: review of VRC data, and adverse event monitoring. If the post-trial visit occurs less than 14 days after the last vaccination, a subsequent follow-up phone call should be made at 14 days post the last dose of trial drug to determine if any adverse events have occurred since the post-trial clinic visit.

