1.0 TRIAL SUMMARY

Abbreviated Title	Safety/Immunogenicity of Different Lots of V114 vs. Prevnar 13™ in Infants
Sponsor Product Identifiers	V114 Generic name not yet assigned
Trial Phase	II
Clinical Indication	Prevention of pneumococcal disease
Trial Type	Interventional
Type of control	Active control without placebo
Route of administration	Intramuscular
Trial Blinding	Double-blind
Vaccination Groups	Subjects will be randomly assigned to receive V114 Lot 1, V114 Lot 2, or Prevnar 13™ (control). See Section 5.2 for a detailed description of the V114 lots).
Number of trial subjects	Approximately 1,050 subjects will be enrolled.
Estimated duration of trial	The Sponsor estimates that the trial will require approximately 2 years from the time that written informed consent is provided for the first subject until the last subject's last study-related phone call or visit. For purposes of analysis and reporting, the overall trial ends when the Sponsor receives the last serological results.
Duration of Participation	Each subject will participate in the trial for approximately 11 to 14 months from the time the parent/legal guardian signs the informed consent form (ICF) through the final contact. Each subject will receive 4 doses of the trial vaccine given at approximately 2, 4, 6, and 12 to 15 months of age. After each vaccination, the trial subject will be observed for 30 minutes and followed for 14 days for injection site and systemic adverse events (AEs). Serious adverse events (SAEs) will be collected from the time the consent form is signed through 30 days post-dose 4 (PD4) and/or completion of the subject's participation in the trial, see Section 7.2 for details. Blood samples will be collected 1 month following dose 3, immediately prior to dose 4, and 1 month following dose 4.
Randomization Ratio	1:1:1

A list of abbreviations used in this document can be found in Section 12.4.

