5.8 Subject Withdrawal/Discontinuation Criteria

5.8.1 Discontinuation of Vaccination

Discontinuation of vaccination does not represent withdrawal from the trial.

As certain data on clinical events beyond vaccination discontinuation may be important to the study, they must be collected until the end of the study, even if the subject has discontinued vaccination. Therefore, subjects who discontinue trial vaccination prior to completion of the vaccination will still continue to participate in the trial as specified in Section 6.0 - Trial Flow Chart and Section 7.1.5.3 – Discontinued Subjects Continuing to be Monitored in the Trial. Subjects who discontinue after Visit 4 (due to lack of efficacy or other reasons) are not required to continue to be monitored and will not be requested to return for a final monitoring visit.

Subjects may discontinue treatment at any time for any reason or be dropped from vaccination at the discretion of the investigator should any untoward effect occur. In addition, a subject may be discontinued from vaccination by the investigator or the Sponsor if vaccination is inappropriate, the trial plan is violated, or for administrative and/or other safety reasons. Specific details regarding procedures to be performed at vaccination discontinuation are provided in Section 7.1.4 – Other Procedures.

A subject must be discontinued from vaccination but continue to be monitored in the trial for any of the following reasons:

- The subject or subject's legally acceptable representative requests to discontinue vaccination.
- The subject's treatment assignment has been unblinded by the investigator, Merck subsidiary or through the emergency unblinding call center.
- The subject has a medical condition or personal circumstance which, in the opinion of the investigator and/or sponsor, placed the subject at unnecessary risk from continued administration of study drug/vaccine.

For subjects who are discontinued from vaccination but continue to be monitored in the trial, see Section 6.0 – Trial Flow Chart, and Section 7.1.5.3 – Discontinued Subjects Continuing to be Monitored in the Trial for those procedures to be completed at each specified visit.

Discontinuation from vaccination is “permanent.” Once a subject is discontinued, he/she shall not be allowed to restart vaccination.

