6.0 TRIAL FLOW CHART

Visit Number:	1 ^l	2 ^{a, l}	3 ^l	4 ^l	5 ^l	6 ^l
Visit Timing:	Age:~2 months DOSE 1	Age:~4 months DOSE 2	Age:~6 months DOSE 3	~1 month after Visit 3	Age:~12 to 15 months DOSE 4	~1 month after Visit 5
Visit Window^j:	≥42 days of age to ≤90 days of age	4 months of age to 1 day prior to 5 months of age	6 months of age to 1 day prior to 7 months of age	28 to 42 days PD3	12 months of age to 1 day prior to 16 months of age	28 to 42 days PD4
Administrative Procedures						
Informed Consent ^b	X					
Informed Consent for Future Biomedical Research (FBR) ^c	X					
Inclusion/Exclusion Criteria	X					
Subject Identification Card	X					
Medical History	X					
Update Medical History (New condition not already recorded as medical history or adverse events)		X	X	X	X	X
Prior Medication ^m	X					
Concomitant Medication Review		X	X	X	X	X
Vaccination Allocation/Randomization in IRT ^d	X					
Trial Vaccine Administration ^d	X	X	X		X	
Childhood Vaccines ^e	X	X	X		X	
Provide Electronic Vaccination Report Card (VRC)	X					
Review VRC data ^f		X	X	X		X
Clinical Procedures/Assessments						
Full Physical Examination	X	X	X		X	
Obtain Temperature ^g	X	X	X		X	
30 Minutes Postvaccination Observation Period ^k	X	X	X		X	
Adverse event Monitoring ^l	X	X	X	X	X	X
Assess for Serious Adverse events ^l	X	X	X	X	X	X
Laboratory Procedures/Assessments						
Collect blood samples for immunogenicity assays (4-5 mL) ^h				X	X ⁱ	X
Collect Buccal Swabs for Future Biomedical Research ^c	X					

- a. For all vaccination visits (Visits 1, 2, 3 and 5), trial coordinator should review the electronic Vaccination Report Card (VRC) in the vendors database at 14 days postvaccination (0 to plus 5 day window) and call the parent/legal guardian if there is a need to address questions (document phone call in trial chart). The site will review VRC with parent/legal guardian at next visit.
- b. Consent must be obtained prior to any trial procedures.
- c. Informed consent for future biomedical research samples must be obtained before the collection of the buccal swab DNA samples. Buccal swab DNA samples for analysis should be obtained prior to the vaccination, on Day 1, on randomized subjects only, or at a later date as soon as the informed consent is obtained.

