- d. In order to avoid bias, the unblinded trial personnel will have no further contact with trial subjects for any trial-related procedures/assessments following administration of the trial vaccines. This includes all safety follow-up procedures. Contact between subjects and unblinded trial personnel after vaccination administration is strictly prohibited. The study vaccine should be removed from the refrigerator no more than 1 hour before vaccination and time of removal and time of vaccination should be noted in subject's chart.
- e. Concomitant (or routine pediatric) vaccines are to be given according to recommended schedule. Any injectable concomitant vaccines provided at the visit must be given after the trial vaccine and in a separate limb, may be given during the 30-minute observation period, and do not require additional observation time. Concomitant oral vaccines may be administered prior to the trial vaccine and other injectable concomitant vaccine.
- f. Adverse events (serious and non-serious) are to be reported from Day 1 to 14 days following each vaccination. Serious Adverse events are to be reported from treatment/randomization through 30 days following the last study vaccination.
- g. Pre-vaccination temperatures taken by trial staff at Visits 1, 2, 3 and 5. Subjects who have febrile illness (rectal temperature $\geq 38.1^{\circ}\text{C}$ [$\geq 100.5^{\circ}\text{F}$] or axillary temperature $\geq 37.8^{\circ}\text{C}$ [$\geq 100.0^{\circ}\text{F}$]) occurring at or within 72 hours of Visits 1, 2, 3 and 5 must be rescheduled. Parent/legal guardian to measure and record temperature per VRC instructions.
- h. Leftover serum samples collected from the main trial will be stored for future use if the FBR consent is signed.
- i. Collect blood prior to vaccination.
- j. Day of first trial vaccination = Day 1 of trial. To calculate visit windows for subsequent trial vaccinations, confirm subject DOB and ensure the age of the subject will fall within the appropriate age range for each trial visit.
- k. Start and stop time for the 30 minute post vaccination observation period must be noted in subject chart.
- l. Subjects who discontinue the study early may be asked to return for a post-trial visit, see Section 7.1.5.3 for details.
- m. Record prior medications taken by the subject within 30 days before first vaccination.

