7.2.2 Immediate Reporting of Adverse Events to the Sponsor

7.2.2.1 Serious Adverse Events

A serious adverse event is any adverse event occurring at any dose or during any use of Sponsor's product that:

- Results in death;
- Is life threatening;
- Results in persistent or significant disability/incapacity;
- Results in or prolongs an existing inpatient hospitalization;
- Is a congenital anomaly/birth defect;
- Is an other important medical event.

Note: In addition to the above criteria, adverse events meeting either of the below criteria, although not serious per ICH definition, are reportable to the Sponsor in the same timeframe as SAEs to meet certain local requirements.

- Is a cancer;
- Is associated with an overdose.

Refer to [Table 2](#) for additional details regarding each of the above criteria.

For the time period beginning when the consent form is signed until treatment allocation/randomization, any serious adverse event, or follow up to a serious adverse event, including death due to any cause, that occurs to any subject must be reported within 24 hours to the Sponsor if it causes the subject to be excluded from the trial, or is the result of a protocol-specified intervention, including but not limited to washout or discontinuation of usual therapy, diet, placebo treatment or a procedure.

For the time period beginning at treatment allocation/randomization through 30 days following the last study vaccination, any serious adverse event, or follow up to a serious adverse event, including death due to any cause, whether or not related to the Sponsor's product, must be reported within 24 hours to the Sponsor either by electronic media or paper. Electronic reporting procedures can be found in the EDC data entry guidelines. Paper reporting procedures can be found in the Investigator Trial File Binder (or equivalent).

Additionally, any serious adverse event brought to the attention of an investigator who is a qualified physician at any time outside of the time period specified in the previous paragraph also must be reported immediately to the Sponsor if the event is either:

1. A death that occurs prior to the subject completing the trial, but outside the time period specified in the previous paragraph.

or

2. A serious adverse event that is considered by an investigator who is a qualified physician to be vaccine related.

All subjects with serious adverse events must be followed up for outcome.

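### For infants who discontinue under Section 7.1.5.3, the last scheduled contact is about day 14 after the last vaccination, but SAEs are reportable through day 30

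*Combined protocol and SAP*

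**What the plan says.** **Reporting window.** Section 7.2.2.1 sets it: "For the time period beginning at treatment allocation/randomization through 30 days following the last study vaccination", covering all SAEs whatever their cause. Note f of the Trial Flow Chart (Section 6.0) agrees: "Serious Adverse events are to be reported from treatment/randomization through 30 days following the last study vaccination". The Trial Summary (Section 1.0) is looser and runs collection "through 30 days post-dose 4 (PD4) and/or completion of the" infant's participation. Section 4.2.3.2 has the same looser phrase, but it refers the reader to 7.2.2.1, and its safety-monitoring text places completion at 30 days after the last dose.

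**Contact schedule.** Under Section 7.1.5.3, an infant who discontinues after Visit 1, 2, 3 or 5, agrees to monitoring and returns for the final visit "will be required to return to clinic approximately 14 days after the last vaccination for the post-trial visit". If that visit comes early, "a subsequent follow-up phone call should be made at 14 days post the last dose of trial drug". Infants who discontinue after Visit 4 have no final visit. Flow-chart note l sends early discontinuers to 7.1.5.3. For completers the last contact is Visit 6, at "28 to 42 days PD4".

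**Text pointing to longer follow-up.** Section 5.8.1 separates stopping vaccination from leaving the trial. It says of certain clinical-event data that "they must be collected until the end of the study, even if the subject has discontinued vaccination", and then refers to both the flow chart and 7.1.5.3. Section 7.1.4.1 asks that infants who stop vaccination early be encouraged to attend the rest of the schedule.

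**Analysis.** Any SAE is a Tier 2 endpoint with 95% confidence intervals for the group differences (Section 8.6.2, Table 4). The safety population is every randomized infant who received trial vaccine (Section 8.5.2), and Section 8.9.2 expects all of them to be evaluable.

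**The concern.** The day-14 call in 7.1.5.3 shows that contact was meant to match the reporting window, and it does so for the 14-day adverse event window. Nothing does the same for the 30-day SAE window. If an infant on the normal schedule has an SAE on day 20, the site asks about it at the next visit. If an infant on the 7.1.5.3 path has the same event, it is recorded only if someone volunteers it.

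Safety is the first primary objective. An event missed in this way leaves the numerator while the infant stays in the denominator, so the SAE proportion can only be understated. Because 5.8.1, 7.1.4.1 and 7.1.5.3 read differently, sites could also follow different rules for similar infants.

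**Working it through.** **1. The plan's own SAE figures.** Section 8.9.2 gives three, and all reproduce with 350 infants per group:

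- Upper 97.5% bound with no events: 1 − 0.025^(1/350) = 1.048%, or 1 in 95.4 (stated: below 1.05%, 1 in 95).
- Chance of at least one event at a rate of 1/217: 1 − (1 − 1/217)^350 = 80.1% (stated: 80%).
- At 1/505: 1 − (1 − 1/505)^350 = 50.0% (stated: 50%).

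These figures take every infant as fully observed.

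**2. Days without a scheduled contact.** Uncovered days = max(0, 30 − day of last scheduled contact), counted from the last vaccination.

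| Last scheduled contact | Source | Uncovered days | Share of the 30 days |
|---|---|---|---|
| Day 14 (final visit or call) | 7.1.5.3 | 30 − 14 = 16 | 53% |
| Day 28 (Visit 6) | Flow chart | 30 − 28 = 2 | 7% |
| Day 29 (Visit 6) | Flow chart | 30 − 29 = 1 | 3% |
| Days 30 to 42 (Visit 6) | Flow chart | 0 | 0% |

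Infants who discontinue after Visit 4 were last due at 28 to 42 days after dose 3, so their gap is also at most 2 days.

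**3. Whether another planned contact fills days 15 to 30.** Flow-chart note a has the site review the electronic report card at day 14 with up to 5 days' allowance, so by day 19 at the latest. The card collects events for 14 days only, and a call follows only if there are questions. Even a call on day 19 would leave 30 − 19 = 11 days.

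**4. What the 53% refers to.** It is the share of the 30 days after the last dose. The whole SAE window starts at randomization. Taking doses at 2, 4 and 6 months of age and about 30.4 days per month, the 16 days are:

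- about 53% of the window after dose 1 (16/30);
- about 18% after dose 2 (16/91, with 91 = 61 + 30);
- about 11% after dose 3 (16/152, with 152 = 122 + 30);
- 4 to 5% after dose 4 at 12 to 15 months.

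**5. Effect on precision (illustration only).** The documents give no discontinuation rate. Suppose 5%, 10% or 15% of 350 were not followed to day 30. The zero-event bound on the remaining 332, 315 or 298 infants would be 1.10%, 1.16% or 1.23% instead of 1.05%. This gives partly observed infants no weight, so it overstates the loss. The weakness is in ascertainment more than in precision.

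**The case against.** The strongest reply is that many of these infants are seen after day 14. Section 7.1.4.1 wants those who stop vaccination to keep attending, 5.8.1 points to the flow chart as well as to 7.1.5.3, and the flow chart assesses SAEs at every visit. An infant who stops after dose 1, 2 or 3 and keeps attending is seen well beyond day 30. Section 7.1.4.1 also calls for final-visit activities when an infant leaves the trial, so an exit made known after day 14 brings a later contact. This stands, and it limits the point to infants whose follow-up ends at the 7.1.5.3 contact. It does not remove the point, because 7.1.4.1 only encourages attendance while 7.1.5.3 describes a final visit at about day 14.

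A second reply is that 7.2.2.1 is a reporting duty, not a visit schedule. Families hold a card with site contact details, SAEs must be followed to outcome, and vaccine-related SAEs are reportable even outside the window. This is correct. What is missing is scheduled contact, not the duty to report. But passive reporting for some infants and direct questioning for others is unequal ascertainment.

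A third reply is that the Trial Summary's wording lets collection end when participation ends. Sections 7.2.2.1 and flow-chart note f state day 30 without that exception, and 4.2.3.2 defers to 7.2.2.1.

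A reader might also infer that the SAE comparison between arms is biased. The documents do not support that: they give no discontinuation rates by arm, 5.8.1 keeps infants stopped for a medical risk under monitoring, and Section 8.6.2 sets no 30-day window for the Tier 2 SAE comparison.

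**Conclusion.** The mismatch is in the text. For infants who discontinue after Visits 1, 2, 3 or 5 and follow 7.1.5.3, the last 16 of the 30 days after the last vaccination have no scheduled contact, although SAEs remain reportable and the infants stay in the safety denominator. This assumes that the visit or call takes place at about day 14 and that no later visit is attended.

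Three stronger readings do not hold. The gap does not apply to every discontinued infant. The 53% is not a share of the whole SAE window, except for infants who stop after dose 1. The completer gap is minor: 1 or 2 days, and only when Visit 6 falls on 2 of its 15 permitted days.

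The number of infants affected and any difference between arms cannot be derived from the documents. The primary immunogenicity analysis is not affected. The point is a cheap improvement in safety ascertainment, worth making because sites cannot tell from the present text which follow-up applies.

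**What to change.** - Reconcile 5.8.1, 7.1.4.1, 7.1.5.3 and 7.2.2.1 so that they state one follow-up for infants who stop vaccination and one for infants who leave the trial.
- Extend the call rule in 7.1.5.3. If a discontinued infant still being monitored has a last contact before day 30 after the last vaccination, make one SAE call on or after day 30. The same call can cover a Visit 6 on day 28 or 29.
- Correct the reference in the opening text of Section 7.2, which gives 7.2.3.1 for the SAE timeframe. The table of contents lists no such section, and the timeframe is in 7.2.2.1.

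The cost is a few amended sentences and one phone call for each family concerned, with no new visit or sample. For every infant reached, the uncovered time falls to 0 days. The call does not help infants who are lost to follow-up or whose consent is withdrawn.
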